5. STUDY DESIGN

5.1. Summary of Study Design

The study is randomized clinical trial. The duration of the study is 2 years. Patients will be screened to confirm they meet study criteria. Consent will be obtained from the legal authorized representative. Initial demographic data will be obtained using REDCap Database. Patients will be randomized to either Oral Methadone tablets or Non-Methadone group. The control group will receive usual care with IV Fentanyl or hydromorphone per hospital protocols as on appendix 1. Patients on the methadone group will be started on Methadone 5mg, 10mg or 15mg every 8 hours depending on Fentanyl drip rate (0-100mcg/hr, 100-200mcg/hr or >200mcg/hr) or hydromorphone drip rate (0-1.5mg/hr, 1.5-3mg/hr, or >3mg/hr). The rate of Fentanyl or hydromorphone will be reduced by 25% initially. If patients require additional sedation later, this will be administered per usual care and the total amount of additional opioids will be documented and used for analysis as morphine milligram equivalents (MME). Likewise, patients could be weaned more than 25% if they showed signs of tolerance to lesser sedation.

At Subsequent encounters: Rate of Fentanyl or Hydromorphone drip will be reduced by 25% every 24 hours until the patient is extubated from the ventilator.

Continuous IV opioids for analgesia for patients on mechanical ventilation is routine clinical care and will not be denied to patients. Once patients are extubated oral methadone will be discontinued and patient monitored for any opioid withdrawal symptoms and treated per protocol as shown on appendix 2 based on their clinical opiate withdrawal scale (COWS) appendix 4. For those with a score of less than 25 oral methadone will no longer be required. For those with a COWS score of >25 methadone will be resumed for a short taper of 3 days. The above can be illustrated as on study protocol flow on Appendix 5 and details on methadone taper as on Appendix 2.

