Monitor for S/Sx of Withdrawal:
Abdominal cramps, diarrhea, nausea, and/or
vomiting. Lacrimation, diaphoresis,
shivering, and piloerection. Mydriasis,
hypertension and tachycardia, irritability,
insomnia, agitation, restless leg syndrome,
tremor
OR

Clinical Opiate Withdrawal Scale

Can be wrenched into vital signs flowsheet.

Goal COWS < 25

Methadone Taper

Consider for patients requiring higher opioid infusion doses or expected prolonged wean. Caution w/ hepatic impairment. Monitor QTc, PO:IV 2:1

Oral Equivalent Taper Consider if

hydromorphone infusion <1.5 mg/hr or fentanyl <150 mcg/min

morphone	Oxycodone
)-90 mg	80-240 mg
)-60 mg	50-150 mg

Opioid Infusion

Wean by 25% per day. Once at low dose, transition to standing IV at equivalent dose or intermittent bolus dosing (0.5-2mg prn q2-4h)

If continuous infusions are unable to wean off, consider uptitrating initial oral replacement dose. Once infusions are off x24 hours, initiate planned taper by decreasing total daily replacement medication by 10-30% every 24-48 hours (see example).

If S/Sx of Withdrawal or COWS ≥ 25:

Consider use of adjunctive agents (clonidine).

Treat symptoms of withdrawal w/ pm bolus doses (0.5-2mg) IV or PO

Remain at same dose or increase to previous dose until signs/symptoms are well-controlled (COWS <25) for 12-24 hours.

Then restart/continue taper.

Example PO Methadone Taper Start taper once infusion off x 24 hours

Methadone 10 mg q8h x48 hours Methadone 7.5 mg q8h x48 hours Methadone 5 mg q8h x48 hours Methadone 5 mg q12h x 24-48 hours Methadone 2.5 mg q12h x24-48 hours

If tapering multiple agents, consider staggering taper on opposite days

Example PO Hydromorphone Taper Start taper once off infusion x24 hours

Hydromorphone 8 mg q4h x48 hours Hydromorphone 6 mg q4h x48 hours Hydromorphone 4 mg q4h x24-48 hours Hydromorphone 4 mg q6h x24-48 hours Transition to intermittent do sing

If tapering multiple agents, consider staggering taper on opposite days

Equianalgesic Doses		Metabolism/Elimination	Additional	
Hydromorphone	IV: 1.5mg / PO 7.5mg	Hepatic metabolism via glucuronidation to inactive metabolites	Least affected by renal or hepatic impairment	
Fentanyl	IV: 100 mcg	Hepatic metabolism via 3A4 to inactive metabolites	Half life increases with obesity and prolonged use	
Morphine	IV: 10 mg/PO: 30 mg	Hepatic metabolism to active metabolites which are renally cleared	Avoid in renal dysfunction, may cause histamine release	

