- Do not abruptly discontinue methadone hydrochloride tablets in a physically dependent patient because rapid discontinuation of opioid analgesics has resulted in serious withdrawal symptoms, uncontrolled pain, and suicide. (2.8, 5.15)

Initiation of Detoxification and Maintenance Treatment

 A single dose of 20 to 30 mg may be sufficient to suppress withdrawal syndrome. (2.7)

-----DOSAGE FORMS AND STRENGTHS----

Tablets: 5 mg and 10 mg (3)

- Significant respiratory depression (4)
- Acute or severe bronchial asthma in an unmonitored setting or in the absence of resuscitative equipment (4)
- Known or suspected gastrointestinal obstruction, including paralytic ileus (4)
- Hypersensitivity to methadone (4)

----WARNINGS AND PRECAUTIONS-

- Risk of Life-Threatening Respiratory Depression in Patients with Chronic Pulmonary Disease or in Elderly, Cachectic, or Debilitated Patients: Monitor closely, particularly during initiation and titration. (5.8)
- Serotonin Syndrome: Potentially life-threatening condition could result from concomitant serotonergic drug administration. Discontinue methadone hydrochloride tablets if serotonin syndrome is suspected. (5.9)
- Adrenal Insufficiency: If diagnosed, treat with physiologic replacement of corticosteroids, and wean patient off of the opioid. (5.10)
- Severe Hypotension: Monitor during dose initiation and titration.
 Avoid use in patients with circulatory shock. (5.11)
- Risks of Use in Patients with Increased Intracranial Pressure, Brain Tumors, Head Injury, or Impaired Consciousness: Monitor for sedation and respiratory depression. Avoid use of methadone hydrochloride tablets in patients with impaired consciousness or coma. (5.12)

-ADVERSE REACTIONS-

Most common adverse reactions are: lightheadedness, dizziness, sedation, nausea, vomiting, and sweating. (6)

To report SUSPECTED ADVERSE REACTIONS, contact Mallinckrodt at [name] or FDA at [name] or www.fda.gov/medwatch.

-DRUG INTERACTIONS-

- Antiretroviral Agents: May result in decreased efficacy or, in certain cases, increased toxicity. (7)
- Potentially Arrhythmogenic Agents: Pharmacodynamic interactions may occur. Monitor patients closely for cardiac conduction changes. (7)
- Mixed Agonist/Antagonist and Partial Agonist Opioid Analgesics: Avoid use with methadone hydrochloride tablets because they may reduce analgesic effect of methadone hydrochloride tablets or precipitate withdrawal symptoms. (5.15, 7)

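### After extubation, Section 5.1 and the Appendix 2 it relies on differ on stopping methadone, taper length and the withdrawal-score trigger, and 5.1 has no branch for a score of exactly 25

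*Combined protocol and SAP*

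**What the plan says.** **Section 5.1** sets the rule in the protocol body. On stopping: "Once patients are extubated oral methadone will be discontinued". Patients are then watched for withdrawal and "treated per protocol as shown on appendix 2 based on their clinical opiate withdrawal scale (COWS) appendix 4". Two score branches follow: "For those with a score of less than 25 oral methadone will no longer be required", and "For those with a COWS score of >25 methadone will be resumed for a short taper of 3 days". The section closes by pointing to Appendix 5 for the flow and to "details on methadone taper as on Appendix 2".

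**Appendix 2** (Opioid Weaning) says that, once infusions have been off for 24 hours, staff should "initiate planned taper by decreasing total daily replacement medication by 10-30% every 24-48 hours (see example"). Its trigger for slowing or reversing that taper is "If S/Sx of Withdrawal or COWS ≥ 25". Its listed actions include adjunctive drugs, bolus doses, and holding or raising the dose until control has lasted 12–24 hours, after which the taper continues.

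**Appendix 3** (product label, highlights; similar text in label sections 2.6 and 5.15): "Do not abruptly discontinue methadone hydrochloride tablets in a physically dependent patient". Label section 2.6 adds that people with briefer opioid use may tolerate a faster taper.

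**Section 4.2** counts extubation among the events that complete the study for a patient. **Appendix 6** nevertheless has a field for the COWS score after extubation.

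**The concern.** Section 5.1 does not treat Appendix 2 as background. It makes that appendix the source for withdrawal treatment and for the taper, and Section 7.1 bases dose selection on it as well. A nurse or physician who follows 5.1 stops methadone when the tube comes out. One who follows the referenced appendix steps it down on a clock that starts when the infusion has been off for a day. The two texts also differ on how long a taper lasts and on what finding triggers action.

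Two things are at stake. The first is patient safety during opioid withdrawal, which Section 2.4 lists among the anticipated adverse events. The second is interpretability. If methadone is stopped in some patients and stepped down in others, the post-extubation COWS scores and withdrawal events do not describe one defined treatment. Section 4.2 adds to this, because it leaves unclear whether those observations fall inside the study at all.

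**Working it through.** **1. The rules side by side**

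| Item | Section 5.1 | Appendix 2 |
|---|---|---|
| Methadone at extubation | Discontinued | No rule tied to extubation; step-down starts after 24 h off infusion |
| Does the taper depend on a score? | Yes, only above 25 | No; it is planned for all |
| Length | 3 days | 10–30% every 24–48 h; five-step example |
| Trigger for action | COWS above 25 | Withdrawal signs or symptoms, or COWS 25 and above |
| Score of exactly 25 | No branch | Covered |

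**2. Can the 3 days (72 h) be found in the Appendix 2 example?** The step durations are 48, 48, 48, 24–48 and 24–48 h.

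- From the top step (10 mg q8h): 48 + 48 + 48 + (24 to 48) + (24 to 48) = 192 to 240 h, or 8–10 days. Ratio to 72 h: 192/72 = 2.7 and 240/72 = 3.3.
- From 7.5 mg q8h: 48 + 48 + (24 to 48) + (24 to 48) = 144 to 192 h, or 6–8 days.
- From 5 mg q8h: 48 + (24 to 48) + (24 to 48) = 96 to 144 h, or 4–6 days.
- From the first q12h step: (24 to 48) + (24 to 48) = 48 to 96 h. This range includes 72 h, but 5.1 gives methadone every 8 hours and says nothing of changing the interval.

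No entry at an 8-hourly step gives 3 days. The highest starting dose in 5.1, 15 mg every 8 hours, lies above the example's first step.

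**3. Can 3 days be found in the percentage rule?** Dose left after the cuts made in 72 h:

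- Fastest, 30% every 24 h, three cuts: 1 − 3 × 0.30 = 0.10 if each cut is a share of the starting dose; 0.70³ = 0.34 if compounding.
- Slowest, 10% every 48 h, one cut: 0.90. To reach zero as a share of the starting dose takes 10 cuts × 48 h = 480 h, or 20 days.

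Three days to zero appears only at the fastest corner: 30% of the starting dose, cut daily, with the first cut made at once, so that dosing runs at 70%, 40% and 10% and then stops. Section 5.1 does not say that this corner is meant.

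**4. Could the Appendix 2 taper already be finished at extubation?** Eligibility requires more than 72 h of ventilation. Taking day 5 from intubation as 5 × 24 = 120 h, a patient extubated by then has had at most 120 − 72 = 48 h of methadone, against 192 h for the shortest full example. For later extubations there is more time, but 5.1 reduces only the infusion before extubation and describes no methadone taper in that period.

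**5. The score of 25.** The 11 COWS items in Appendix 4 have maxima 4, 4, 5, 5, 4, 4, 5, 4, 4, 4 and 5, which sum to 48. A total of 25 is attainable: four items at 5, one at 4 and one at 1 give 20 + 4 + 1. Appendix 4 places 25 at the bottom of its 25–36 band. The branches in 5.1 omit exactly this one value; those in Appendix 2 omit none.

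**6. How many patients.** 80 randomised 1:1 gives 40 on methadone. At the assumed 50% extubated by day 5, that is 0.50 × 40 = 20 patients by day 5, plus those extubated later.

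**7. Timing against Section 4.2.** The order of events is extubation, study completion, COWS assessment, then any taper. The Appendix 6 field is therefore filled after the point at which 4.2 calls the patient's study complete.

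**The case against.** The strongest reply is that Appendix 2 is another hospital's general guidance. It says it should be adapted to the individual patient, its schedule is labelled an example, and its weaning criterion is at least 7 days of use, whereas this trial excludes patients with more than 5 days of IV analgesia. A specific protocol rule can reasonably sit beside such guidance, and the 3-day taper in 5.1 is a resumption after stopping, not the planned step-down of the appendix. Staff also receive a month of training on tapering and withdrawal. The gap at 25 is a single value that the appendix covers. The label warning applies only to physically dependent patients, and label section 9.3 says clinically significant dependence may take days to weeks to develop.

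Much of this stands. The 8–10 days should be read as the length of an example, and the label supports the point without being a clear contradiction. But 5.1 does not say that it overrides Appendix 2. It names Appendix 2 as the source of the taper details, and no 3-day schedule is set out there. Training cannot settle the matter while the text to be taught gives two procedures. The Appendix 5 figure might show the intended sequence, but it could not be checked; even if it does, the written passages would still disagree.

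**Conclusion.** The point holds as a conflict between the trial's own written rules. Section 5.1 and Appendix 2 differ on whether methadone stops or is stepped down, on taper length (3 days against 8–10 days in the example) and on the trigger; 5.1 leaves a score of 25 unassigned; and 4.2 completes the study before these steps occur. The stop-or-taper difference reaches every extubated methadone patient, about 20 of 40 by day 5 if the 50% assumption is met. The cut-offs themselves differ at one score only, although Appendix 2 also acts on symptoms alone.

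A reader might infer more than the documents support:

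- *That the day-5 result is compromised.* Extubation comes before these rules apply, so there is no direct effect. The sample size is also untouched.
- *That withdrawal would arise only in the methadone arm.* Controls also enter after more than 72 h of opioid infusion and are weaned.
- *That it would lengthen stay or cause reintubation.* Nothing in the protocol's account of the trial says so.
- *That differing practice between the hospitals would bias the comparison.* Randomisation is stratified by site, so such differences would mainly add variability.
- *That patients scoring 13–24 are wrongly left without treatment.* Section 5.1 refers to Appendix 2, which acts on symptoms; whether the threshold itself is right is a clinical question outside this point.

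The conclusion assumes that Appendix 2 is binding where 5.1 refers to it.

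**What to change.** Reconcile Section 4.2, Section 5.1, Appendix 2 and the Appendix 5 flow figure into one written post-extubation rule. It should state what happens to methadone at extubation, which taper applies and where its steps are set out, and a cut-off that assigns every COWS score, including 25. It should say whether Appendix 2 governs or is superseded where the two differ, and should take account of the appended label text. Section 4.2 should make clear whether the post-extubation COWS record and any taper fall within study participation. The clinical team and the DSMB decide the content.

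The cost is a wording amendment with its IRB review and an updated staff briefing at both hospitals. The post-extubation COWS field is already on the data sheet. No new assessment schedule, extra patients or change to the primary analysis is needed.

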6. METHODS AND ASSESSMENTS

Based on the assumptions of successful extubation by day 5 of 50% of patients in the methadone group and 20% of patients in the control group and using a two tailed alpha level of 5%, a power of 80% our sample size calculation comparing proportions of two groups yielded 76. A 5% fallout as correction factor was 4 leaving us with a sample size of 80 patients. Statistical methods will include descriptive statistics and time to event analysis. Baseline characteristics will be reported. Data will be collected on a data collection sheet prior to transfer to REDCAPs database (Appendix 6). We will generate Kaplan-Meier curves and for comparison of hazard between groups we will use Cox regression (Cox proportional hazards model). Patients who die will be censored at time of death. Time of weaning will take into consideration only patients who were permanently disconnected from the ventilator. QTc values will be obtained from patient monitors and documented on data collection tool daily.

Randomization tables will be generated using REDCAPs database by study statistician. At the end of the study recorded information from REDCAPs will be exported to STATA for statistical analysis.

#UTHealth Houston

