2.5 Outcomes

a. Primary

Proportion of patients on methadone that get extubated by day number 5 from the date of intubation

b. Secondary

Proportion of patients that develop prolonged QTC after administration of methadone. Others will be ICU length of stay, ICU mortality, hospital length of stay and hospital mortality.

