3.3. Inclusion Criteria

Patients will be enrolled only if they consented and they meet all of the inclusion criteria listed below.

- 1. Patients 18 years or older
- 2. Patients on IMV for more than 72 hours
- 3. Patients infused Fentanyl or Hydromorphone for more than 72 hours
- 4. Patients with evidence of reversal of process that caused respiratory failure, adequate oxygenation (PaO2/FIO2>200; Positive end expiratory pressure (PEEP)≤8 and Ph≥7.2
- 5. Patients hemodynamically stable
- 6. Patients with a failed single or multiple attempts at spontaneous breathing trials

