3.4. Exclusion Criteria

All subjects meeting any of the exclusion criteria at baseline will be excluded from participation.

- 1. Patients with history of opioid drug abuse
- 2. Patients receiving schedule II narcotics on a chronic basis for longer than 6 months prior to ICU admission or on other analgesic infusions other than Fentanyl or Hydromorphone
- 3. Patients with cervical spinal cord injury or neuromuscular disease
- 4. Patients with end stage liver disease at ICU admission (ie, International normalized ratio ≥2and not taking warfarin and/or a total serum bilirubin ≥1.5 times above normal limits
- 5. Patients with prolonged QTc interval ≥500
- 6. Patients with prior history of cardiac conduction defects or suddendeath
- 7. Patients with QTc increase of ≥60 milliseconds above the value of prior EKGs measured during current ICU admission
- 8. Patients with more than 5 days on IV analgesia
- 9. Patients intubated for more than 30 days
- 10. Patients without feeding tubes
- 11. Patients not receiving enteral feeding
- 12. Exclusion of patients in a comatose state
- 13. Exclusion of patients in Status Epilepticus
- 14. Exclusion of post-operative patients

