Bone or Joint aches If patient was having pain previously, only the additional component attributed to opiates withdrawal is scored O not present mild diffuse discomfort patient reports severe diffuse aching of joints/muscles patient is rubbing joints or muscles and is unable to sit still because of discomfort	Gooseflesh skin 0 skin is smooth 3 piloerrection of skin can be felt or hairs standing up on arms 5 prominent piloerrection			
Runny nose or tearing Not accounted for by cold symptoms or allergies 0 not present 1 nasal stuffiness or unusually moist eyes 2 nose running or tearing 4 nose constantly running or tears streaming down cheeks	Total Score The total score is the sum of all 11 items Initials of person completing assessment:			

Score: 5-12 = mild; 13-24 = moderate; 25-36 = moderately severe; more than 36 = severe withdrawal This version may be copied and used clinically.

Journal of Psychoactive Drugs

[figure not shown]
Volume 35 (2), April - June 2003

Source: Wesson, D. R., & Ling, W. (2003). The Clinical Opiate Withdrawal Scale (COWS). J Psychoactive Drugs, 35(2), 253–9.

Appendix 5

Protocol Flow

Appendix 6

#UTHealth Houston

Data Collection Tool

Patient Identification Code (MRN):

Baseline Characteristics Age (years) Sex		
Sex		
Race		
Weight (Kg)		
Duration on ventilator at time of		
randomization (Hours)		
	Pneumonia = 1	
, , ,	Aspiration = 2	
	Non-Pulmonary Sepsis = 3	
	COPD Exacerbation = 4	
	Other Causes = 5	
Assessments and Measurements	Other Causes - 5	
APACHE II Score		
Total SOFA Score		
Tidal Volume ml/kg of predicted		
body weight		
Peep at time of enrollment (cm H2O)		
PaO2: FIO2 ratio (mmHg)		
FiO2 at time of enrollment		
Duration on mechanical ventilation		
before start of weaning(hours)		
Last recorded Ph prior to enrollment		
Duration in ICU stay after enrollment		
(Hours)		
Mean QTc while on Methadone		
Clinical Opiate Withdrawal Scale		
(COWS) after extubation		
Adverse Event		
Medication Parameters		
Fentanyl Initial Dose (mcg/hour)		
Fentanyl accumulated dose(mcg)		
Days on Fentanyl before start of		
weaning		
Hydromorphone initial Dose		
(mg/hour)		
Hydromorphone accumulated		
dose(mg)		
Days on Hydromorphone before		
start of weaning		
Dexmedetomidine accumulated		
dose(mcg)		
Midazolam accumulated dose(mg)		
Propofol accumulated dose (mg)		
Ketamine accumulated dose (mg)

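### The planned test of the day-5 outcome ignores hours ventilated at randomisation and hospital; it stays valid, but gives up precision and protection against chance imbalance

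*Combined protocol and SAP*

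**What the plan says.** - **Outcome.** Section 2.5 takes as primary the proportion of patients who "get extubated by day number 5 from the date of intubation". The sample size (Sections 6 and 10.1) is built on this proportion, so I treat it as the primary comparison.
- **Entry.** Section 3.3 requires "Patients on IMV for more than 72 hours". Section 3.4 excludes "Patients with more than 5 days on IV analgesia" and "Patients intubated for more than 30 days".
- **Analysis.** Section 10.2 names a chi-squared test for categorical variables. The sentence sits among the interim-analysis text, but no other test for a proportion appears anywhere. Section 6 adds Kaplan-Meier curves and says that "for comparison of hazard between groups we will use Cox regression (Cox proportional hazards model"). No covariate, stratified test or time origin is given, and baseline characteristics are only to be reported.
- **Randomisation.** Sections 4.1 and 6.1 stratify by hospital only.
- **Data collected.** Appendix 6 has, under its baseline block, a row beginning "Duration on ventilator at time of" and ending with randomisation, in hours. "APACHE II Score" is listed under a different block, for assessments and measurements.

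The documents never use the word unadjusted; that is inferred from the methods named.

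**The concern.** The clock for the primary outcome starts at intubation, but nobody is randomised until at least 72 hours later. With day 5 taken as 120 h, a patient randomised at 73 h has 47 h left to be extubated in time, and one randomised at 108 h has 12 h. The link between this baseline value and the outcome therefore comes from the protocol's own definitions; only its strength has to be assumed.

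Nothing in the design balances hours ventilated between arms, and nothing in the analysis uses it. Hospital is balanced by design and then dropped from the analysis. In an open-label trial of 80 patients, a visible imbalance in hours would put the investigators in a bind. Adjusting after the fact would look data-driven, and not adjusting would leave a result that readers could put down to entry time.

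**Working it through.** **Inputs from the documents:** 50% v 20% extubated by day 5, two-sided 5%, 80% power, 76 patients, 80 after 5% dropout (Section 10.1); 1:1 allocation (Section 4.1); entry after 72 h (Section 3.3).

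**Assumptions:** day 5 = 120 h; entry uniform over 72-120 h or over 72-96 h; constant extubation rate after entry, calibrated to average 20% and 50%.

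**1. The plan's own figure.** Pooled formula: n = [1.96√(2×0.35×0.65) + 0.8416√(0.25+0.16)]² / 0.30² = 38.48 per arm, rounded to 39, total 78. Arcsine formula: h = 1.5708 − 0.9273 = 0.6435; n = 2×7.849/0.6435² = 37.9, rounded to 38, total 76. The stated 76 reproduces, and 76 + 4 = 80. It is sized for a plain comparison of two proportions, with power 79.5% at 38 per arm and 81.6% at 40.

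**2. Outcome probability by entry hour.** P(extubated by 120 h, entry at t) = 1 − exp[−λ(120 − t)]. Averaged over entry at 72-120 h this is 1 − (1 − e^(−48λ))/(48λ). Setting it to 20% and 50% gives λ = 0.00967 and 0.0332 per hour.

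| Entry (h) | Hours left | Control | Methadone |
|---|---|---|---|
| 73 | 47 | 36.5% | 79.0% |
| 96 | 24 | 20.7% | 54.9% |
| 108 | 12 | 11.0% | 32.9% |
| 119 | 1 | 1.0% | 3.3% |

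**3. Size of a chance imbalance.** SD of entry time = 48/√12 = 13.9 h. At 38 per arm the SE of the difference in means = 13.9×√(2/38) = 3.2 h, so the 95% range is about ±6.2 h, in a window of at most 48 h.

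**4. Power at 38 per arm,** chi-squared v logistic likelihood-ratio test adjusted for entry time:

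| Entry range | Unadjusted | Adjusted | Gain |
|---|---|---|---|
| 72-120 h | 80% | 86% | about 5-6 points |
| 72-96 h | 80% | 81% | about 0-1 point |

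A separate set of 4,000 simulated trials gave 79% v 85% and 80% v 81%. The Monte Carlo SE at that number is √(0.8×0.2/4000) = 0.6 points per figure.

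**5. Type I error.** Across simulations the unadjusted test rejected a true null in 4.1% to about 5% of trials, and the test adjusted for entry time in 4.7-5.9%.

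**6. What an imbalance does when it occurs.** With no true effect (35% in both arms, 38 per arm, entry over 72-120 h, 40,000 trials), about 9% of trials had a 5-7 h imbalance. In those the observed risk difference moved by about 7 points on average toward the earlier-entering arm, and the unadjusted test rejected about 8.5% of the time. With an imbalance under 1 h it rejected about 3.4%. The overall rate stays near 5%.

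**7. Room for covariates.** Expected events: 38×0.50 + 38×0.20 = 26.6, about 27.

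**The case against.** The strongest reply is that a randomised comparison needs no adjustment to be valid: chance imbalance is already allowed for in the 5% error rate. That stands. A reader might infer from step 6 that the planned test is biased or inflates type I error. It does neither, because the 8.5% is conditional on an unlucky allocation and is offset by lower rates elsewhere.

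Three further objections also stand and limit the point.

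- **Cox model.** A reader might carry the time-left argument straight over to Section 6. The documents do not support that. The Cox model is not said to stop at day 5, participation can run to 30 days (Section 4.2), and the time origin is not stated. If time runs from randomisation, the mechanical link is gone. If it runs from intubation, hours already ventilated are delayed entry, not an ordinary covariate.
- **APACHE II.** It is tempting to call it a baseline covariate left unused. Appendix 6 lists it beside post-randomisation items (mean QTc on methadone, COWS after extubation) and gives no scoring time, whereas PEEP and FiO2 in the same block are tied to enrolment.
- **Root cause.** Hours ventilated matters this much because the clock starts before randomisation. The 30-day intubation limit does not bar entry after 120 h. The five-day analgesia limit does not either if the infusion began after intubation. Such patients cannot change outcome status, and no covariate repairs that.

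What does not stand is the inference that adjustment is therefore pointless: it costs almost nothing and is credible only if fixed in advance.

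**Conclusion.** The point holds as a missed gain in precision, not as a flaw in validity. The plan's test of the day-5 outcome omits a baseline value that fixes the time left to reach that outcome, and omits the factor used to stratify randomisation. Both are available without new data.

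The gain in power at 38 per arm is about 0-1 point to about 5-6 points. It depends on how widely entry times spread, on which the documents are silent, and on a constant extubation rate. The omission is certain; the size of the benefit is not. The gain from including hospital is not quantified here. If the outcome clock were moved to randomisation, the mechanical link would disappear, and the value of adjusting for hours would depend on a prognostic strength that the documents do not give.

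**What to change.** - **Primary analysis.** Pre-specify a logistic model for the day-5 outcome with arm, hospital and hours ventilated at randomisation. Report the standardised risk difference with its 95% CI, and keep the unadjusted chi-squared test as supportive.
- **APACHE II.** Add it only if the protocol defines it as a score taken before randomisation.
- **Cox model.** State the time origin first. If it is randomisation, include hospital and hours ventilated as covariates. If it is intubation, handle hours ventilated as delayed entry.
- **Separately,** reconcile the day-5 clock (Section 2.5) with the entry and exclusion limits (Sections 3.3 and 3.4). The adjusted model does not do this.

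The cost is a few lines of analysis-plan text and a little programming. The downside is small: with about 27 expected events, covariates must be few and fixed before any outcome data are seen, and null rejection may run slightly above 5% (about 5.6-5.9% in one set of simulations).
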